## 9.2.4 Product Quality Complaint Handling

A product quality complaint (PQC) is defined as any suspicion of a product defect related to manufacturing, labeling, or packaging, ie, any dissatisfaction relative to the identity, quality, durability, or reliability of a product, including its labeling or package integrity. A PQC may have an impact on the safety and efficacy of the product. Timely, accurate, and complete reporting and analysis of PQC information from studies are crucial for the protection of subjects, investigators, and the sponsor, and are mandated by regulatory agencies worldwide. The sponsor has established procedures in conformity with regulatory requirements worldwide to ensure appropriate reporting of PQC information; all studies conducted by the sponsor or its affiliates will be conducted in accordance with those procedures.

### 9.2.4.1 Procedures

All initial PQCs must be reported to the sponsor by the study-site personnel within 24 hours after being made aware of the event.

If the defect is combined with a SAE, the study-site personnel must report the PQC to the sponsor according to the SAE reporting timelines (refer to Section 9.2.1). A sample of the suspected product should be maintained for further investigation if requested by the sponsor.

### 9.2.4.2 Contacting Sponsor Regarding Product Quality

The names (and corresponding telephone numbers) of the individuals who should be contacted regarding product quality issues are listed on the Contact Information page(s), which will be provided as a separate document.

## 10. END OF TREATMENT

A patient may be discontinued from study treatment at any time if the patient, the Investigator, or the Sponsor feels that it is not in the patient's best interest to continue on study. If a patient's study treatment must be discontinued, this will not result in automatic withdrawal of the patient from the study.

The following is a list of possible reasons for early discontinuation of study treatment:

- Disease progression (*patients should be highly encouraged to stay on study treatment until there is BICR-confirmed radiographic progression; treatment decisions should not be based on PSA alone*)
- Any episode of seizure
- Any other adverse event that cannot be adequately managed with dose modifications, including dose interruption for  $\geq 28$  days may require study drug discontinuation, which must be discussed with the Sponsor.
- Protocol violation requiring discontinuation of study treatment
- Patient is not compliant with study procedures
- Lost to follow-up
- Patient withdrawal of consent

- Sponsor request for early termination of study

All patients discontinuing study treatment will enter the Long-term Follow-up Phase and will be followed for the development of symptomatic progression and initiation of subsequent anti-cancer therapies every 4 months until death, loss of follow-up, or withdrawal of consent, whichever comes first.

If a patient is lost to follow-up, every reasonable effort must be made by the study site personnel to contact the patient and determine the reason for discontinuation/withdrawal. The measures taken to follow up must be documented.

When a subject withdraws before completing the study, the reason for withdrawal is to be documented in the CRF and in the source document. Study drug assigned to the withdrawn subject may not be assigned to another subject. Subjects who withdraw will not be replaced.

Data to be collected for the end of treatment visit are described in Section 8.7. Patients will be followed for at least 28 days after the last dose of study drug. If a patient is withdrawn from treatment due to an adverse event, the patient will be followed until the adverse event has resolved or stabilized as per Section 9.2.

For information on subsequent therapy with abiraterone acetate see Section 8.10

## 11. PROTOCOL VIOLATIONS

A protocol violation occurs when the patient or Investigator fails to adhere to significant protocol requirements affecting the inclusion, exclusion, patient safety and primary endpoint criteria. Protocol violations for this study include, but are not limited to, the following:

- Failure to meet inclusion/exclusion criteria [*no waivers will be granted to meet the eligibility criteria*]
- Use of a prohibited concomitant medication
- Dose modifications that are not within the protocol specifications
- Any other deviation that presents significant risk or safety concerns to the patient

Failure to comply with Good Clinical Practice (GCP) guidelines will also result in a protocol violation. The Sponsor, in consultation with the Investigator, will determine if a protocol violation should result in withdrawal of a patient.

## 12. DATA MONITORING COMMITTEE

An Independent Data Monitoring Committee (IDMC) will be established to monitor data on an ongoing basis to ensure the safety of the subjects enrolled in this study. The committee will meet periodically to review interim safety data. After the review, the IDMC will make recommendations regarding the conduct of the study. The IDMC will serve as the primary reviewers of the efficacy analysis. Further details will be provided in a separate IDMC charter.

The IDMC will consist of at least 2 medical experts in the relevant therapeutic area and at least 1 statistician. The IDMC responsibilities, authorities, and procedures will be documented in the IDMC charter.

## 13. STATISTICAL METHODS AND CONSIDERATIONS

A detailed methodology for summary and statistical analyses of the data collected in this study will be documented in a Statistical Analysis Plan (SAP) that will be dated, version-controlled and maintained by the Sponsor.

### 13.1 ANALYSIS POPULATIONS

**Full Analysis (Intent-to-Treat) Population [ITT]:** All eligible patients who are randomized into the study, with study drug assignments designated according to initial randomization, regardless of whether patients receive study drug or receive a different drug from that to which they were randomized to will be included in the analyses of all efficacy and clinical benefit endpoints and patient characteristics.

**Safety Analysis Population [SAFETY]:** All patients who receive at least one dose of study drug, with treatment assignments designated according to actual study treatment received will be the primary population for evaluating safety and treatment compliance and administration.

- **Patient Report Outcomes Population [PRO]:** Subset of the safety analysis population that has completed at least the baseline assessment (Cycle 1 Day 1) of either FACT-P or EQ-5D questionnaires.
- **Population Pharmacokinetics Populations [PK]:** Subset of the safety analysis population that was randomized to the apalutamide treatment arm and that has at least one PK sample collected.
- **Biomarker Population:** Subset of the safety analysis populations that has at least 1 biomarker sample collected.

### 13.2 EFFICACY ANALYSES

Efficacy analyses will be performed on the ITT population, incorporating the randomization stratification factors as documented on the CRF, unless otherwise specified.

Analyses of efficacy endpoints which are based on radiographic tumor assessments (MFS, PFS, and TTM) will be based on the results of the BICR. Investigator assessments may be used for sensitivity analyses, as described in the Statistical Analysis Plan.

### 13.2.1 Analysis of Primary Endpoint

The primary endpoint for the study is metastasis-free survival (MFS) which is defined as the time from randomization to first evidence of BICR-confirmed radiographically detectable bone or soft tissue distant metastasis (simply referred to as “metastasis” from this point forward) or death due to any cause (whichever occurs earlier) + 1 day.

The MFS data for patients without metastasis or death will be censored on the date of the last tumor assessment (or, if no tumor assessment was performed after the baseline visit, at the date of randomization + 1 day). Additional censoring rules will vary according to whether the analysis is performed for US or ex-US regulatory purposes, as shown below; both results will be provided in the clinical study report.

Scenario	US regulatory guidance	ex-US regulatory guidance 
Data from patients who are lost to follow-up or whose disease progression (development of metastasis) or death occurs after 2 or more consecutively missing or unevaluable tumor assessments	Censored on the date of the last tumor assessment that the patient was known to be metastasis-free	Time of progression will be determined using the first date when there is documented evidence of progression or death (whichever occurs earlier) regardless of missed or unevaluable tumor assessments
Patients that receive new systemic anti-cancer therapy prior to documented disease progression (development of metastasis) or death	Censored on the date of the last tumor assessment prior to the start of the new systemic anti-cancer therapy	Time of progression will be determined using the first date when there is documented evidence of progression or death (whichever occurs earlier) regardless of change of therapy

The primary efficacy analysis will be completed when approximately 372 MFS events have occurred. The primary analysis will compare the MFS distributions in the two treatment arms using a two-sided log-rank test, stratified by PSADT (> 6 months vs. ≤ 6 months), the use of a bone-sparing agent (Yes vs. No), and the presence of loco-regional disease (N0 vs. N1) at the 0.05 significance level. The unstratified log-rank test will be provided as a sensitivity analysis. A complete list of sensitivity analyses is provided in the Statistical Analysis Plan.

Kaplan-Meier methods will be used to estimate median MFS for each treatment arm. Cox proportional-hazard models, including the same factors as above, will be used to estimate the hazard ratio and its 95% confidence interval (CI). Additional analyses by formulation

subgroups will be performed for the MFS endpoint as described in the Statistical Analysis Plan.

### 13.2.2 Analyses of Secondary Endpoints

For the secondary endpoints, a hierarchical testing will be performed in the following order:

- TTM
- PFS
- Time to symptomatic progression
- OS
- Time to initiation of cytotoxic chemotherapy

each at  $\alpha=0.05$  (2-sided). Each secondary endpoint will have a final analysis but there will be no interim analysis for TTM and PFS. There will be 1 interim analysis for time to symptomatic progression, and up to 2 interim analyses for OS and time to initiation of cytotoxic chemotherapy. The testing of time to symptomatic progression, OS and time to initiation of cytotoxic chemotherapy endpoints will utilize an adaptive group sequential method, according to the pre-specified O'Brien-Fleming-type alpha spending function with possible re-estimation of the required number of events necessary for the next analysis to maintain the desired conditional power. If time to symptomatic progression is significant at the IA, then there will be only 1 interim analysis for OS and time to initiation of cytotoxic chemotherapy; otherwise there will be 2 interim analyses for OS and time to initiation of cytotoxic chemotherapy.

The final analysis of TTM and PFS, interim analysis of time to symptomatic progression, and the first interim analysis of OS and time to initiation of cytotoxic chemotherapy will all be performed at the same time as the primary analysis of MFS (approximately 372 events).

Full details about the adaptive group sequential testing procedure will be provided in the statistical analysis plan.

Time-to-event-based secondary endpoint analyses (TTM, PFS, time to symptomatic progression, OS, and time to initiation of cytotoxic chemotherapy) will be performed using a two-sided log-rank test, stratified by PSADT (> 6 months vs.  $\leq$  6 months), the use of a bone-sparing agent (Yes vs. No), and the presence of loco-regional disease (N0 vs. N1). Unstratified log-rank tests will also be provided as sensitivity analyses.

Kaplan-Meier methods will be used to estimate medians for each treatment arm. Cox proportional-hazard models, including the same factors as above, will be used to estimate the hazard ratio and its 95% confidence interval (CI). One year, 2-year, 3-year, and 5-year survival rates will be estimated using the Kaplan-Meier method.

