**13.2.2.2 Time to Symptomatic Progression**

Time to symptomatic progression will be defined as the time from randomization to documentation in the CRF of any of the following (whichever occurs earlier) + 1 day:

- Development of a skeletal-related event (SRE): pathologic fracture, spinal cord compression, or need for surgical intervention or radiation therapy to the bone.
- Pain progression or worsening of disease-related symptoms requiring initiation of a new systemic anti-cancer therapy.
- Development of clinically significant symptoms due to loco-regional tumor progression requiring surgical intervention or radiation therapy.

Adverse event, concomitant medication, concomitant treatment, or survival follow-up CRFs will be the source of these findings.

Time to symptomatic progression for patients who do not experience any of the events described above will be censored on the date on which they were last known to be event-free.

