**13.2.2.3 Time to Initiation of Cytotoxic Chemotherapy**

Time to initiation of cytotoxic chemotherapy will be defined as the time from randomization to documentation in the CRF of a new cytotoxic chemotherapy being administered to the patient (e.g., survival follow-up CRF) + 1 day.

Time to initiation of cytotoxic chemotherapy for patients who do not start cytotoxic chemotherapy will be censored on the date of last contact.

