### 13.2.2.5 Time to Metastasis

Time to metastasis will be defined as the time from randomization to first evidence of BICR-confirmed radiographically detectable bone or soft tissue distant metastasis (simply referred to as “metastasis” from this point forward) + 1 day.

Time to metastasis data for patients without metastasis will be censored on the date of the last tumor assessment (or, if no tumor assessment was performed after the baseline visit, at the date of randomization + 1 day). Additional censoring rules will vary according to whether the analysis is performed for US or ex-US regulatory purposes, as shown below; both results will be provided in the clinical study report.

Scenario	US regulatory guidance	ex-US regulatory guidance
Data from patients who are lost to follow-up or whose disease progression (development of metastasis) occurs after 2 or more consecutively missing or unevaluable tumor assessments	Censored on the date of the last tumor assessment that the patient was known to be metastasis-free	Time of progression will be determined using the first date when there is documented evidence of progression regardless of missed or unevaluable tumor assessments
Patients that receive new systemic anti-cancer therapy prior to documented disease progression (development of metastasis)	Censored on the date of the last tumor assessment prior to the start of the new systemic anti-cancer therapy	Time of progression will be determined using the first date when there is documented evidence of progression regardless of change of therapy

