7.5 EFFICACY ANALYSES

The following section outlines the planned analyses of the primary and secondary efficacy outcomes of the study.

Efficacy analyses will be performed on the ITT population, incorporating the randomization stratification factors as documented on the IVRS, unless otherwise specified.

Time-to-event endpoints will be summarized using the Kaplan-Meier method ³ and displayed graphically where appropriate. Median event times and 2-sided 95% confidence interval for each median will be provided. Cox proportional-hazard models, including the stratification factors at baseline, will be used to estimate the hazard ratio (HR) and its 95% confidence interval (CI).

Response endpoints (eg, PSA response rate) will be summarized using descriptive statistics for categorical data by treatment group. The relative risk (treatment:control) will be reported along with the associated 2-tailed 95% CIs. The two treatment groups will be compared using the stratified Mantel-Haenszel test; Fisher's exact test may be used if the expected counts in some cells are small.

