7.5.3.2 Time to Symptomatic Progression

Time to symptomatic progression will be defined as the time from randomization to documentation in the CRF of any of the following (whichever occurs earlier) + 1 day:

- Development of a skeletal-related event (SRE): pathologic fracture, spinal cord compression, or need for surgical intervention or radiation therapy to the bone.
- Pain progression or worsening of disease-related symptoms requiring initiation of a new systemic anti-cancer therapy.
- Development of clinically significant symptoms due to loco-regional tumor progression requiring surgical intervention or radiation therapy.

Adverse event, concomitant medication, or survival follow-up CRFs may also be the source of these findings.

Time to symptomatic progression for patients who do not experience any of the events described above will be censored on the date on which they were last known to be event-free.

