7.5.3.3 Time to Initiation of Cytotoxic Chemotherapy

Time to initiation of cytotoxic chemotherapy will be defined as the time from randomization to documentation of a new cytotoxic chemotherapy being administered to the patient (e.g., survival follow-up CRF) + 1 day.

Time to initiation of cytotoxic chemotherapy for patients who do not start a cytotoxic chemotherapy will be censored on the date of last contact.

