7.5.3.5 Time to Metastasis

Time to Metastasis (TTM) will be defined as the time from randomization to first evidence of BICR-confirmed radiographically detectable bone or soft tissue distant metastasis + 1 day.

ARN-509-003 Statistical Analysis Plan v7.0 26 June 2017

Page 16 of 34

TTM data for patients without metastasis will be censored on the date of the last tumor assessment (or, if no tumor assessment was performed after the baseline visit, at the date of randomization + 1 day). Additional censoring rules will vary according to whether the analysis is performed for US or ex-US regulatory purposes, as shown below; both results will be provided in the clinical study report.

Scenario	US regulatory guidance	ex-US regulatory guidance
Data from patients who are lost to follow-up or whose disease progression (development of metastasis) occurs after 2 or more consecutively missing or unevaluable tumor assessments	Censored on the date of the last tumor assessment that the patient was known to be metastasis-free	Time of progression will be determined using the first date when there is documented evidence of progression regardless of missed or unevaluable tumor assessments
Patients that receive new systemic anti-cancer therapy prior to documented disease progression (development of metastasis)	Censored on the date of the last tumor assessment prior to the start of the new systemic anti-cancer therapy	Time of progression will be determined using the first date when there is documented evidence of progression regardless of change of therapy

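### Symptomatic progression, time to chemotherapy and, to a small extent, TTM censor death but have only Kaplan-Meier absolute summaries; cumulative incidence should be added

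*Protocol*

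**What the plan says.** Three of the five secondary endpoints leave death out of the event definition.

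- **TTM.** Only centrally confirmed distant metastasis counts. Protocol 13.2.2.5: "Time to metastasis data for patients without metastasis will be censored on the date of the last tumor assessment". SAP 7.5.3.5 has the same rule.
- **Symptomatic progression.** Skeletal events, symptom or pain worsening that leads to new systemic treatment, and symptomatic local progression needing surgery or radiotherapy count. Under SAP 7.5.3.2, everyone else "will be censored on the date on which they were last known to be event-free". Protocol 13.2.2.2 agrees.
- **Cytotoxic chemotherapy.** Under SAP 7.5.3.3, patients who never start it "will be censored on the date of last contact". Protocol 13.2.2.3 agrees.

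No sentence says in so many words that death is censored. It follows from the definitions.

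The absolute summaries are Kaplan-Meier. Protocol 13.2.2 says "Kaplan-Meier methods will be used to estimate medians for each treatment arm"; SAP 7.5 says "Time-to-event endpoints will be summarized using the Kaplan-Meier method", with graphs and with medians and their confidence intervals. The 1-, 2-, 3- and 5-year rates stand in the protocol's general secondary-endpoint section, but the SAP places them under overall survival only (7.5.3.1). Neither document mentions competing risks or cumulative incidence. Testing is by stratified log-rank, with Cox hazard ratios.

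**The concern.** A man who dies can no longer metastasise, progress symptomatically or start chemotherapy. Kaplan-Meier with death censored treats him as if he would have gone on to have the event at the survivors' rate. The curve therefore describes a setting in which nobody dies first. It does not describe the share of randomised patients who have the event.

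Readers usually take a Kaplan-Meier curve for time to chemotherapy as that share, and the median as the time by which half the patients have started. On that reading the event risk is too high and the median too early in both arms, by amounts that depend on each arm's event-free mortality. The difference between arms can shift as well. What is at stake is the absolute description of benefit. The hypothesis tests are not at stake.

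**Working it through.** **1. The plan's own figures.** Schoenfeld's formula with 2:1 allocation is events = (z₁ + z₂)² / [(2/3)(1/3)(ln HR)²].
- MFS, HR 0.70, 90% power, two-sided 0.05: 372, as stated in Protocol 13.6.
- Symptomatic progression, 80% power: 427 for HR 0.75 and 191 for HR 0.65, as stated in SAP 7.5.3.

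These targets concern log-rank comparisons of cause-specific hazards. Nothing below changes them.

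**2. Inputs from the documents.** Protocol 13.6 assumes a placebo median MFS of 25 months and a placebo median OS of 49 months (about 65 on apalutamide), with 1,200 patients accrued over 24 months, 75% of them in the second year. The monthly placebo hazards are ln 2/25 = 0.0277 for MFS and ln 2/49 = 0.0141 for OS. Protocol 15.6 puts the MFS analysis about 9 months after last patient in (month 33) and the projected study end near month 65.

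**3. Input not in the documents.** Neither document gives a rate of death before any of the three events. It is varied below.

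**4. Formulas (constant hazards).** With event hazard a and event-free death hazard d:
- 1 − KM = 1 − exp(−a·t)
- cumulative incidence = a/(a + d) × [1 − exp(−(a + d)·t)]

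The first is never below the second. The direction needs no assumption; only the size does.

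**5. Symptomatic progression or chemotherapy.** Here a = ln 2 / (assumed Kaplan-Meier median) and d = f × 0.0141. Worked case, median 60 months and f = 0.5: a = 0.01155 and d = 0.00707. At 60 months 1 − KM = 50.0%, and cumulative incidence = 0.620 × (1 − exp(−1.118)) = 41.7%. Gaps are computed before rounding.

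| KM median (months) | f | 36 months: 1 − KM / cum. inc. / gap | 60 months: 1 − KM / cum. inc. / gap |
|---|---|---|---|
| 40 | 0.25 | 46.4 / 43.9 / 2.5 | 64.6 / 59.3 / 5.3 |
| 40 | 0.5 | 46.4 / 41.5 / 4.9 | 64.6 / 54.6 / 10.1 |
| 60 | 0.1 | 34.0 / 33.2 / 0.8 | 50.0 / 48.2 / 1.8 |
| 60 | 0.25 | 34.0 / 32.1 / 1.9 | 50.0 / 45.6 / 4.4 |
| 60 | 0.5 | 34.0 / 30.3 / 3.7 | 50.0 / 41.7 / 8.3 |
| 60 | 1.0 | 34.0 / 27.1 / 6.9 | 50.0 / 35.3 / 14.7 |
| 100 | 0.25 | 22.1 / 20.8 / 1.3 | 34.0 / 30.9 / 3.1 |
| 100 | 0.5 | 22.1 / 19.6 / 2.5 | 34.0 / 28.1 / 5.9 |

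For the 60-month case, the cumulative-incidence median is about 70 months at f = 0.25, 88 at f = 0.5, and never reached at f = 1.0.

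**6. Difference between arms.** Take a placebo median of 60 months, an event HR of 0.75, and d as the same fraction of each arm's OS hazard (medians 49 and 65). At 60 months Kaplan-Meier shows a difference of 9.5 points. Cumulative incidence shows 8.8, 7.9, 6.6 and 4.6 points at f = 0.1, 0.25, 0.5 and 1.0.

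**7. TTM, placebo arm.** The total MFS hazard is held at 0.0277 and a share s of MFS events is taken to be deaths. Results at 24 months, which suits an analysis at month 33:

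| s | 1 − KM | Cum. inc. | Gap | Median: KM v cum. inc. (months) |
|---|---|---|---|---|
| 5% | 46.9 | 46.2 | 0.7 | 26.3 v 27.0 |
| 10% | 45.1 | 43.7 | 1.3 | 27.8 v 29.2 |
| 20% | 41.3 | 38.9 | 2.4 | 31.2 v 35.4 |
| 30% | 37.2 | 34.0 | 3.2 | 35.7 v 45.2 |

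On apalutamide (MFS median 35.7 months) the 24-month gap runs from 0.4 to 1.8 points over the same shares.

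**The case against.** The strongest reply is about size. Only deaths before the endpoint compete, and the documents never give that rate. Under Protocol 13.6 one expects about 226 deaths (19% of 1,200) at month 33 and 530 (44%) at month 65. A reader might infer substantial competing mortality from these totals, but they include deaths after the event. The nearest evidence points to a low rate. Protocol 3.1.2 cites a cohort in which 90% of deaths were from metastatic prostate cancer, and Protocol 1.1.3 reports no deaths among 51 Phase II patients with non-metastatic disease. Taken at face value, 90% makes pre-metastasis deaths 0.10 × 25/49 = 5.1% of MFS events, which is the 0.7-point row for TTM. That cohort had earlier-stage disease, however, and the figure says nothing direct about symptomatic progression or chemotherapy.

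A reader might also try to take the size from SAP Appendix 1, by pairing 427 symptomatic-progression events with 80% of the maximum deaths. The text does not support this. Appendix 1 gives 0.8 for the final symptomatic-progression analysis, and SAP 7.5.3 lets that analysis fall anywhere from 191 events to X1 + 1.1 × (427 − X1), where X1 is the interim count. Moreover, 427/1,200 is a crude fraction under staggered entry. It is not a cumulative incidence at any time point.

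The second reply is about the target. Kaplan-Meier with death censored displays the same cause-specific hazard that the log-rank test and Cox model compare, so it is wrong only when read as the share of patients with the event. This stands, and it is why Kaplan-Meier should stay.

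Third, TTM is analysed once, at the MFS analysis, with MFS beside it counting death. This stands too. Symptomatic progression and chemotherapy have no death-inclusive counterpart; OS is reported, but it is a different endpoint.

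Last, the SAP plans landmark rates for OS only. The point therefore rests on the curves and medians, and on the protocol's more general sentence about yearly rates.

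**Conclusion.** The point holds as a modest gap in the absolute estimates, mainly for symptomatic progression and time to chemotherapy. Read as the proportion of patients with the event, 1 − KM is too high and the median too early.

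The size rests on constant hazards and on assumed event-free mortality. With a Kaplan-Meier median of 60 months and f between 0.25 and 0.5, the overstatement is about 2 to 4 points at 36 months and 4 to 8 at 60 months. It reaches about 15 points at 60 months only if the event-free death hazard equals the full placebo OS hazard. The 60-month figures matter only at late analyses. For TTM the overstatement is about 1 to 3 points at 24 months if deaths are 5 to 30% of MFS events.

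A reader might infer that the secondary tests are compromised. They are not: with death censored, log-rank and Cox compare cause-specific hazards, and type I error and event targets stand as planned.

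**What to change.** In SAP 7.5 and 7.5.3, and in Protocol 13.2.2:

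- Beside the Kaplan-Meier summaries, add Aalen-Johansen cumulative incidence by arm with 95% confidence intervals for symptomatic progression and chemotherapy, and for TTM. Death without the event is the competing event.
- Report the number of event-free deaths by arm for each endpoint.
- Label the hazard ratios as cause-specific.
- Base any statement about the proportion of patients with the event on the cumulative incidence.

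Leave the stratified log-rank tests, the Cox models, the alpha allocation and the event targets as they are. Kaplan-Meier stays, so the curves still match the tests and remain comparable with other trials.

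The cost is wording in two documents, a standard procedure, and a few extra tables and figures. No new data are needed, because survival status is already collected every 4 months in long-term follow-up (Protocol 8.9). The drawback is that two absolute summaries of the same endpoint will stand side by side, and each needs a clear label.
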